8.8.6.3 Imaging tests

The conduct of imaging tests is acceptable if required to evaluate the status of the lymphoma at any time during the conduct of the study, including during screening for the purpose of assessing eligibility criteria (e.g., exclusion of EATL, which requires the use of the site's standard imaging techniques). These tests may include enteroscopy (videocapsule and double balloon enteroscopy), entero CT scan, MRI (for size of mesenteric lymph nodes; thickness of bowel wall) and 18FDG-PET scan.

The results of imaging tests will be listed for ITT analysis population, if applicable.

8.9 Additional analyses

In addition to the main analyses, pre-specified subgroup analyses may include the following, if reasonable distributions of subgroups are available for statistically meaningful assessments:

- Dietary transgressions (gluten consumption) based on serial iVYLISA GIP testing and on the dietician's assessment;
- Previous RCD-II treatment (e.g. previous treatment with BMT, cladribine, steroids, Hu-Mik-beta1, etc.);
- Duration of disease;
- Age of onset of RCD-II;
- Sex;
- Site;
- Expression of certain biomarkers at baseline, such as CD122, Granzyme B and IL-21R in IELs, or IL-15 in serum;
- Levels of anti-tTG antibodies, at baseline and during the study;
- Protocol deviations: missed doses of IP, incorrect IP volume for administration, etc.;
- Use of immune-suppressants: concomitant or prior to the study (cladribine, azathioprine, budesonide, stem cell transplant, etc.).

These additional sensitivity analyses may be carried out only for the key flow cytometry and histology endpoints (i.e., the primary and secondary efficacy endpoints dependent on biopsy tissue). Separate models will be fitted for males and females, compliant and non-compliant subjects, subjects with each of the previous treatments, groups of subjects with different disease durations, groups of subjects with different age of onset of disease, and for each site. In order to determine whether the effects of sex, compliance and site are statistically significant, additional three models are fitted where compliance, sex and site and their interaction terms with treatment group, respectively, are included.

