where $\mu_{AMG\ 714}$ and $\mu_{placebo}$ denote the mean baseline to Week 12 relative (%) change in % aberrant IELs vs total IELs as assessed by flow-cytometry in the AMG 714 and placebo arm, respectively. The hypotheses will be tested using a two-sided, 0.10 level of significance.

7 Estimation of sample size

The CELIM-RCD-002 study is an exploratory proof-of-concept (POC) study of an experimental medication, AMG 714, in RCD-II patients. While it will be the first such study sponsored by a pharmaceutical company, the straightforward design is based on several academic studies (Goerres *et al*, 2003; Brar *et al*, 2007; Tack *et al*, 2011a, 2011b) as well as on the nonclinical proof-of-principle signal obtained with AMG 714 in intestinal explants from patients with RCD-II (Malamut *et al*, 2010).

The sample size is based on the size of previous academic studies. Published prospective academic studies have ranged from 13 to 18 subjects total (Tack *et al*, 2011a, 2011b) and CELIM-RCD-002 will be the largest prospective trial ever conducted in RCD-II, a very rare malignant disease.

The sample size of 24 subjects (16 subjects in AMG 714 arm and 8 subjects in placebo arm) has been calculated to achieve at least ~ 80% power to detect a 20 percentage point difference in the primary endpoint, the difference in the baseline-to-Week 12 reduction of % aberrant IELs vs total IELs between the AMG 714 arm and placebo arm.

This sample size calculation was based on the following assumptions:

- Two-sided type one error rate $\alpha = 0.1$.
- Power $1-\beta = 0.8$.
- Analysis method: one-way analysis of variance (ANOVA) by SAS[®] (proc power).
- 2:1 allocation ratio between the AMG 714 and placebo arms.
- Common SD = 17.4 for the baseline to Week 12 reduction in % aberrant IELs as assessed by flow-cytometry.

- Mean change of 20 percentage points and 0 percentage points in the baseline to Week 12 reduction in % aberrant IELs in the AMG 714 and placebo arms, respectively.

The standard deviation used for the sample size calculation is computed from the % aberrant IELs (obtained by flow-cytometry) data from 13 subjects treated with cladribine (subset of the subjects reported in Tack et al, 2011).

8 Statistical methods

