8.2 General statistical considerations

Descriptive statistics (e.g. mean, median, standard deviation (SD), minimum (MIN), maximum (MAX), and number of subjects with an observation (N) or missing observation (NMISS)) are used for summarizing continuous variables. Additional statistics will be provided for PK-related data, including the geometric mean, SD of log-transformed data, geometric CV% and geometric N (i.e. number of subjects with an observation that are included in the natural logarithmic transformation).

Frequencies and percentages are used for summarizing categorical variables.

All summary statistics will be presented by treatment arm and if repeated measures, then by visit/collection time point.

All listings will be created using ITT population. The PP and ITT flags for each subject will be included in all listings.

All tests will be two-sided, if not stated differently. P-values smaller than 0.1 (for primary hypothesis) or 0.05 (all other hypotheses) will be considered statistically significant. In addition to the inferential statistics, 90% or 95% confidence intervals will be constructed. For the primary endpoint a 90% confidence interval of the treatment difference will be

constructed. Ninety-five percent (95%) confidence intervals will be constructed for the individual treatment point estimates.

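### SAP 8.9 fits separate subgroup models by previous RCD-II treatment, disease duration and age of onset but plans no interaction test to compare treatment effects between their levels

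*SAP*

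**What the plan says.** SAP 8.9 (Additional analyses) lists ten subgroup factors. They may be analysed if the subgroup distributions are reasonable, and the work may be limited to the flow cytometry and histology endpoints that depend on biopsy.

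The section then describes models for six of the ten. It states: "Separate models will be fitted for males and females, compliant and non-compliant subjects, subjects with each of the previous treatments", and the sentence goes on to disease-duration groups, onset-age groups and each site. The next sentence adds interaction models for three of these six: "In order to determine whether the effects of sex, compliance and site are statistically significant, additional three models are fitted", each containing the factor and its interaction with treatment group. Two of the factors named in the first quote, sex and compliance, are therefore covered. Previous treatment, disease duration and age of onset are not. For the other four listed factors (baseline biomarkers, anti-tTG levels, protocol deviations, immune-suppressant use) no model is described.

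The section calls these analyses pre-specified, and also sensitivity analyses. It stands apart from SAP 8.7, which is the exploratory section, and says nothing about multiplicity. SAP 8.2 sets the general rule: "P-values smaller than 0.1 (for primary hypothesis) or 0.05 (all other hypotheses) will be considered statistically significant".

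**The concern.** Two separate models answer the question of whether there is an effect within each subgroup. They do not answer whether the effect differs between subgroups, which is the question a subgroup analysis is meant to address. The SAP accepts this for sex, compliance and site, where it adds an interaction term to ask about significance. It does not do so for the other three modelled factors, and gives no reason for the difference.

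With 24 subjects split in two, significance in one part and not in the other is a common chance result even when the drug works equally well in both. Previous treatment is a factor where such a result could attract attention. Exclusion criterion 5 in the Protocol Synopsis allows entry to subjects naive to cladribine and transplant, and, if at least six months have passed since either, to non-responders, relapsers and incomplete responders. What is at stake is a mistaken belief about who benefits. The primary test is not affected.

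**Working it through.** **Inputs.** From SAP section 7: 16 versus 8 subjects, common SD 17.4 and "Mean change of 20 percentage points and 0 percentage points in the baseline to Week 12 reduction in % aberrant IELs" in the two arms, so a difference of 20 points on the absolute scale. The primary test is two-sided at 0.10. From SAP 8.2: 0.05 for all other hypotheses, taken here to cover subgroup and interaction tests. Assumed, because the documents give no subgroup sizes: a two-level factor that splits the trial 12/12, with 8 versus 4 in each half.

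**1. The plan's own power.** SE = 17.4 × √(1/16 + 1/8) = 7.53. Noncentrality = 20/7.53 = 2.65, with 22 df. Noncentral-t power at two-sided 0.10 is 0.823. This agrees with the stated value of at least about 80%, so the inputs are read correctly.

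**2. Power within one half.** SE = 17.4 × √(1/8 + 1/4) = 10.66. Noncentrality = 20/10.66 = 1.88, with 10 df. Power at two-sided 0.05 is p = 0.397.

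**3. Chance that exactly one half is significant when the true effect is the same in both.** The halves share no subjects, so the probability is 2p(1 − p) = 2 × 0.397 × 0.603 = 0.479. Losing one df to the baseline covariate gives p = 0.389 and 0.475. Simulation with random 12/12 splits gave 0.46 to 0.48.

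**4. Dependence on the true effect** (12/12 split, 0.05):

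| True uniform effect (points) | Power per half | Exactly one half significant |
|---|---|---|
| 0 | 0.050 | 0.095 |
| 10 | 0.136 | 0.235 |
| 15 | 0.247 | 0.372 |
| 20 | 0.397 | 0.479 |
| 25 | 0.563 | 0.492 |
| 30 | 0.719 | 0.404 |

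**5. Dependence on the split** (20 points, 0.05). For 16/8 subjects (11 v 5 and 5 v 3), the two powers are 0.510 and 0.265, and p₁(1 − p₂) + p₂(1 − p₁) = 0.505. For 18/6 subjects (12 v 6 and 4 v 2), they are 0.579 and 0.178, giving 0.551. Unequal subgroups make it slightly worse.

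**6. The interaction test on the same data.** SE = 17.4 × √(1/8 + 1/4 + 1/8 + 1/4) = 17.4 × √0.75 = 15.07, with 20 df. With a uniform effect it is significant 5% of the time, by construction. If the effects in the two halves truly differ by 20 points, noncentrality is 20/15.07 = 1.33 and power at 0.05 is 0.244.

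**The case against.** The strongest reply is that the SAP never says a subgroup effect will be declared when one level is significant and the other is not. It says only that separate models will be fitted, and where it asks about the significance of a factor it uses interaction models. That is correct. A reader might infer that subgroup effects are to be judged by comparing p-values, but the text contains no such rule, so the 48% is conditional on someone reading the output that way. What remains is that, for these three factors, the plan offers no other comparison between levels.

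A reader might also infer that most of the modelled factors lack an interaction test. The documents do not support this: of the six with separate models, three have one.

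Nor should the chance findings be counted at 0.10, or added up over every model in the section. SAP 8.2 reserves 0.10 for the primary hypothesis. A count over all models would include sex and site, which have interaction models, and very small cells that the condition on reasonable distributions may rule out.

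The context also softens the point. SAP section 7 calls the trial an exploratory proof-of-concept study, and 8.9 is optional and conditional. The go/no-go rule in Protocol 13.1 rests on the two Immunological Responses and uses no subgroup result. Selection of a later population from these analyses is a possibility that the documents do not mention. All this limits the consequences, but none of it supplies the missing comparison: an even 12/12 split, about the best distribution available, still gives the 48%.

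**Conclusion.** The concern holds as a specific gap. For previous RCD-II treatment, disease duration and age of onset, SAP 8.9 plans separate models and no interaction, so it has no valid way to say whether the treatment effect differs between levels. The section's labels and the 0.05 rule in SAP 8.2 leave the resulting p-values open to being read as findings.

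If they were compared, a uniform effect at the design values would look specific to one half about 48% of the time at 0.05, against 5% with an interaction test. This rests on a true effect of 20 points, SD 17.4, normal errors and an assumed even two-level split; over true effects from 0 to 30 points the figure runs from 9.5% to 49%.

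There are two limits. The inputs are on the absolute scale, whereas the SAP's primary endpoint is relative (%) change, for which no SD is given. The calculation also does not apply to site, which has several levels (about 5 to 6 sites planned), or to prior-treatment groups as the SAP forms them, because one subject may have had several prior therapies and the groups can overlap.

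**What to change.** For previous treatment (each prior therapy coded yes/no), disease duration and age of onset, where subgroup sizes allow, fit one model per factor in all PP subjects. It should contain treatment, factor, treatment-by-factor and the baseline value of the endpoint, extending the approach already planned for sex, compliance and site. Report the interaction estimate and the within-level treatment effects with confidence intervals. Add a sentence that the analyses in 8.9 are exploratory, have no multiplicity control and support no claim of significance.

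The cost is a few lines of SAP text and minor programming; data collection and trial conduct do not change. The drawback is low interaction power, about 24% at 0.05 for a 20-point difference in effect with a 12/12 split. A non-significant interaction will therefore not show that the effect is uniform, which is why the intervals and the exploratory label are needed along with the test.

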Appendix 1. Study schedule

Appendix 2. List of tables and figures

Appendix 3. List of subject data listings

Appendix 4. Table templates

12 Document history

Version number	Version date	Status	Author
1.0	24OCT2016	Final	[name]
2.0	16JUN2017	Final	[name]

Changes and additions made in SAP V2.0

Additions

1. Sensitivity analysis of absolute change from baseline added to the following endpoints:
 - a. Change from baseline in the % of aberrant IELs vs total IELs as assessed by flow-cytometry;
 - b. Change from baseline in the % of aberrant IELs vs intestinal epithelial cells;
 - c. Change from baseline in VH:CD ratio;
 - d. Change from baseline in total IEL counts.
2. The following additional sensitivity analyses which might be carried out if deemed appropriate, were added:
 - a. Levels of anti-tTG antibodies, at baseline and during the study;
 - b. Protocol deviations: missed doses of IP, incorrect IP volume for administration, etc.;
 - c. Use of immune-suppressants: concomitant or prior to the study (cladribine, azathioprine, budesonide, stem cell transplant, etc.);
 - d. If a subject had a misallocated treatment on a specific visit, observed upon unblinding, a secondary sensitivity analysis will be performed on as treated basis;
 - e. Sensitivity analysis excluding atypical subjects from all efficacy assessments.
3. The following exploratory analyses were also added:
 - a. Averages by treatment for proportion of subjects showing BSSF ≥ 6 by time will be plotted. The differences in treatment AUCs will be explored using one-way analysis of variance;
 - b. Week 12 PGA scores will be dichotomized for an outcome endpoint where scores ≤ 2 will be considered treatment success and scores > 2 will be considered treatment failure. Assessment of differences in treatment proportions will be conducted;

- c. A tabulation of the proportion of subjects with at least a 50% change from baseline for ≥ 6 weeks in CeD PRO will be provided.
4. The following hematology parameters were added:
 - a. Basophils/Leukocytes;
 - b. Eosinophils/Leukocytes;
 - c. Lymphocytes/Leukocytes;
 - d. Monocytes/Leukocytes;
 - e. Anti -tissue transglutaminase (tTG) IgA and IgG;
 - f. Anti-tTG6 IgA and IgG.
5. Serum Granzyme B (pg/mL) was added to the list of biomarkers of disease activity to be analyzed.
6. Additionally, shift table of liver function tests (Aspartate Aminotransferase (AST), Alanine Aminotransferase (ALT), Bilirubin (Total) and Alkaline Phosphatase (ALP)) will be created. Count and frequencies by treatment group will be presented in the shift table.
7. Major protocol deviations will be tabulated and summarized by treatment group in addition to listing these.
8. Definition of relative change from baseline was added.

Changes

1. The total GSRS score will be calculated as the mean (not sum as specified in SAP V1.0) of the scores of all 15 questions, with the scores for the individual questions between 1 (No discomfort at all) and 7 (Very severe discomfort).
2. The total CeD-GSRS score will be calculated as the mean (not sum as specified in SAP V1.0) of scores of all 10 questions in CeD-GSRS questionnaire, with the scores of the questions between 1 (No discomfort at all) and 7 (Very severe discomfort).
3. The definition of change from baseline was given in more detail.
4. It was decided, that in addition to other imputations, all assay results over the upper limit of quantification (ULOQ) will be assigned a value of ULOQ.
5. The individual overlaid figures were deemed unnecessary and therefore were removed from SAP V2.0 with the exception of overlaid individual curves of CeD PRO.
6. The analysis of resolution of mucosal atrophy according to Marsh scores was removed.
7. Analysis of subjects with normalization of total IEL counts by immunochemistry was removed.
8. Analysis of immunohistochemistry IL-15 positive cells was removed.
9. Referral to PK Data Analysis Plan was replaced with PK Report (PK Data Analysis Plan will not be created).
10. Minor changes to wording were made (e.g. typos corrected, wording clarified).
